## 6.2 Endpoints and Related Variables

### 6.2.1 Primary Endpoint

Objective	Endpoint
To assess the efficacy of imetelstat for the treatment of AML and MDS patients failing or being refractory to first line hypomethylating agent (HMA)-based treatment	Overall hematological response rate as assessed in week ████████ of treatment with imetelstat using the combined response assessment criteria for MDS and AML (see Appendix 11.2 for more details). The main analysis will be based on the eCRF item “Is the subject classified to be a Responder according to protocol?” (RS_DSRESP).

### 6.2.2 Secondary Endpoints

Objective	Endpoint
-----------	----------

To assess the safety of imetelstat	
Toxicity is measured by TEAEs (see section 7.7.12), which will be coded using the MedDRA coding system (see section 7.5.1). All SOC's are rated by NCI CTCAE v5.0.
 
Early toxicity will be estimated by toxicity until visit 3 (W5 C2).
 
Time to first related TEAE with toxicity of grade 3 or higher.

To assess efficacy of imetelstat	
Overall survival is defined as the time from the beginning of imetelstat treatment until death or censored at the date of the last observation in the study.
 
Progression-free-survival is defined as the duration of time from time of imetelstat treatment to time of progression or death, whichever occurs first. A subject who has neither progressed nor died will be censored on the date of the last observation.
 
Duration of best overall response measured from the time measurement criteria are met for CR, Cri, PR or SD (whichever is first recorded, defined in section 11.2 Appendix 2 a)) until the first date at which recurrent or progressive disease is objectively documented.
 
Best overall response is defined as the best response recorded from the start of the imetelstat treatment until disease progression (taking as reference for progressive disease the smallest measurements recorded since the treatment started).

To assess efficacy of imetelstat in the MDS population.	
For MDS population only:
 
Response based on IWG 2023 criteria (for definition see section 11.2 Appendix 2 b))

To assess efficacy of imetelstat.	
Quality of life is measured using the scores of EORTC QLQ-C30 (version 3)
 
 
Global health status / QoL
 

	
 
• Functional scales
 
• Symptom scales / items
 

--	---

### 6.2.3 Other Endpoints

Endpoint

Vital signs
 
 
• Height (in cm)
 
• Weight (in kg)
 
• BMI (in kg/m^2)
 
• Systolic blood pressure [SBP] (in mmHg)
 
• Diastolic blood pressure [DBP] (in mmHg)
 
• Pulse rate (in beats/min)
 
• Respiratory rate (breaths/min)
 
• Body temperature (in °C)
 
 
Physical examination (Normal/ Abnormal, nCS/ Abnormal, CS) for each body system
 
 
• General appearance
 
• Head – Eyes – Ears – Neck – Throat
 
• Skin
 
• Musculoskeletal system
 
• Lymph nodes
 
• Nervous system
 
• Chest
 
• Abdomen
 
• Spine and limbs
 
 
Laboratory parameters:
 
 
• Serum chemistry
 

- Sodium (in mmol/L)
- Potassium (in mmol/L)
- Chloride (in mmol/L)
- Bicarbonate (if available) (in mmol/L)
- Calcium (in mmol/L)
- Magnesium (in mmol/L)
- Phosphate (in mmol/L)
- Urea nitrogen (in mmol/L)
- Creatinine (in mmol/L)
- Glomerular Filtration Rate, Estimated (in ml/min/1.73 m^2)
- Glucose (in mmol/L)
- Albumin (in mmol/L)
- Protein (in g/L)
- Alkaline phosphatase (in nkat/L)
- Bilirubin (in mmol/L)
- Aspartate Aminotransferase (in nkat/L)
- Alanine Aminotransferase (in nkat/L)
- Urate (in mmol/L)
- Gamma Glutamyl Transferase (in mmol/L)
- Automated complete blood count
  - Erythrocytes (T/L)
  - Leukocytes (in G/L)
  - Neutrophils (in 10^9/L)
  - Eosinophils (in G/L)
  - Basophils (in G/L)
  - Lymphocytes (in G/L)
  - Monocytes (in G/L)

- Haemoglobin (in g/dL)
- Haematocrit (in %)
- Nucleated Erythrocytes (in T/L)
- Reticulocytes (in T/L)
- Platelets ( $10^9/L$ )
- Ery. Mean Corpuscular Volume (in fL)
- Ery. Mean Corpuscular Hemoglobin (in fmol)
- Ery. Mean Corpuscular HGB Concentration (in mmol/L)
- Erythrocytes Distribution Width (in %)
- Cytogenetic Analysis
  - Number of metaphases available for analysis (<20 or  $\geq 20$ )
  - Karyotype (according to IPSS-R-Score: very good, good, intermediate, poor, very poor))
- BM Cytology Assessment
  - Blasts in Bone Marrow (in %)
  - Auer Rods (in %, not detectable is set to 0%)
  - Ringed Sideroblasts (in %, not detectable is set to 0%)
  - Dysplasia (>10% Dysplasia in Erythropoiesis (yes/no), >10% Dysplasia in Thrombopoiesis (yes/no), >10% Dysplasia in Granulopoiesis (yes/no))
- CBC with differential:
  - Neutrophils/Leukocytes (in %)
  - Promyelocytes/Leukocytes (in %)
  - Myelocytes/Leukocytes (in %)
  - Metamyelocytes/Leukocytes (in %)
  - Eosinophils/Leukocytes (in %)
  - Basophils/Leukocytes (in %)
  - Lymphocytes/Leukocytes (in %)

 
○ Monocytes/Leukocytes (in %)
 
• PB blast assessment
 
○ Blasts (in %)
 

Transfusion history by type of transfusion (RBC, platelets, see 7.7.2 for derivation):
 
 
• Number of units within ■ weeks before treatment and after first dose
 
• Rate of units within ■ weeks before treatment and after first dose
 
• Mean pretransfusion levels (g/dL for RBC, mL for platelets) within ■ weeks before treatment and after first dose
 

Exposure to imetelstat:
 
 
• Treatment compliance defined as number of doses until visit ■ divided by number of doses for ■ cycles.
 
• Duration of treatment (in days)
 
• Total dose (in mg), defined as the sum of all total calculated dose administrated until visit ■.
 
• Dose intensity as dose level administrated (■)
 

Additional parameters:
 
 
• ECOG Performance status (from 0= Fully active, able to carry on all pre-disease performance without restriction to 5 = Dead)
 

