9.3 Documentation and reporting of AE/SAE

All subjects will be monitored for AEs during the study by the study personnel. Assessments may include monitoring of any or all of the following parameters: the subject's clinical symptoms, laboratory, pathological, radiological or surgical findings, physical examination findings, or findings from other tests and/or procedures.

The investigator must assess all abnormal laboratory results for their clinical significance. If any abnormal laboratory result is considered clinically significant, the investigator must provide details about the action taken with respect to the test drug and about the event's outcome. All laboratory values have to be signed by the investigator.

For adverse events reporting the medical diagnosis must be reported. In case the diagnosis is not available, individual symptoms can be reported to fulfill reporting timelines. If a diagnosis becomes available at a later stage, it must be added to the reported event. In cases of surgical or diagnostic procedures, the condition/illness leading to such a procedure is considered as the AE rather than the procedure itself. In case of a fatality, the cause of death is considered as the AE, and the death is considered as its outcome. The Investigator shall make every effort to obtain a copy of the autopsy report and or death certificate and transmit this, after anonymization, to the sponsor.

Any medical condition that is present at the time that the participant is screened will be considered as baseline and not reported as an AE. However, if the study participant's condition deteriorates at any time during the study, it will be recorded as an AE.

All AEs (for example observed AEs, AEs mentioned upon open questioning by a member of the investigator's team or spontaneously reported AEs by the subject) will be recorded by the Investigator from the time the subject signs informed consent until 28 (\pm 5) days after the EOT visit (i.e. TEAEs) as well as those SAEs made known to the Investigator at any time thereafter that are suspected of being related to IMP (i.e. SADRs).

If the AE onset is prior to the first dose of IMP and the event does not increase in severity after initiation of IMP, the AE is then considered to be a pre-treatment AE and will not be reported in the TEAE incidence tables.

If the onset is prior to the first dose of IMP and the severity increases thereafter, the event is documented as a TEAE.

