10.9.2 Extent of Exposure

Duration of treatment, total dose and dose intensity will be summarized. Dose modifications will also be summarized if applicable. Details will be provided in the SAP.

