#### **7.7.3 Duration of treatment**

Duration of treatment (DoT, in days) will be defined as the time elapsed from the start of treatment (date of administration at cycle ■, week ■) to the date of treatment discontinuation (TD) or the last available date with drug administration (LD):

$DA$  ■ = Drug administration date in Visit ■ [YYYY-MM-DD]

$DoT [days] = \min(TD, LD) - DA$  ■

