### 8.5.3 Extent of exposure

Duration of treatment (see 7.7.3), treatment compliance, total dose and dose intensity (see 6.2.3) will be summarized with descriptive statistics overall. Dose intensity will be summarized by cycle and by overall mean in a subject level. Dose modifications will be listed separately.

Table	
14.8.1	Extent of exposure
Listing	
16.8.1	Extent of exposure
16.8.2	Dose modifications

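### Total dose stops at a fixed visit while treatment duration in the same exposure table runs to the last infusion, so total dose is understated for any patient dosed after that visit

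*SAP*

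**What the plan says.** Protocol 10.9.2 asks for three exposure summaries and sets no time window: "Duration of treatment, total dose and dose intensity will be summarized". It leaves the details to the SAP.

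SAP 6.2.3 supplies them. Total dose is "Total dose (in mg), defined as the sum of all total calculated dose administrated until visit", followed by a blacked-out number. In the same cell, compliance starts "Treatment compliance defined as number of doses until visit" (number also blacked out) and is divided by the doses for a fixed number of cycles.

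SAP 7.7.3 measures duration of treatment from first administration "to the date of treatment discontinuation (TD) or the last available date with drug administration (LD"), taking the earlier of the two dates. No visit ends it.

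SAP 8.5.3 puts the measures together in Table 14.8.1, on the Safety Evaluation Set: "Duration of treatment (see 7.7.3), treatment compliance, total dose and dose intensity (see 6.2.3) will be summarized with descriptive statistics overall". Dose intensity is given by cycle and as a subject-level mean.

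Protocol 9.3 has adverse events recorded until 28 (±5) "days after the EOT visit (i.e. TEAEs"), and the overall TEAE tables in SAP 8.5.1 have no visit cut-off. SAP 6.1 describes the extension phase as running from cycle 5 until response is lost, so it has no fixed end.

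**The concern.** Someone reading Table 14.8.1 will take total dose as what patients received over the duration reported beside it. Under the SAP's definitions the two figures describe different periods once a patient is dosed beyond the cut-off visit, and nothing in either document labels the total as primary-phase only. Where the SAP wants a restricted window elsewhere it names it: early toxicity in 6.2.2 is tied to visit 3.

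This matters for reading the safety results. Protocol 7.2.2.1 links the frequency and severity of cytopenias to dose intensity, so readers will look to the exposure table for context. Results are also shown by cohort (SAP 8.5). The SAP document history records no responders at the interim analysis, and under the regimen in Protocol 7.1.1 non-responders went to end of treatment. Dosing past the cut-off therefore probably falls mainly in Cohort 2, whose total dose would look low relative to Cohort 1. That last step is an inference, not something the documents state.

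**Working it through.** The documents give no total-dose figure, so the check is a dose count from the schedule.

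**Inputs**
- Visit map: V3 = week 5 (SAP 6.2.2), V5 = week 9 and V9 = week 17 (SAP 8.3). Hence visit k falls in week 2k − 1.
- Primary phase: two-weekly (SAP 2.1.2), one dose per visit.
- V9 is itself a dosing visit, because treatment continues until the response result is available (Protocol VII, footnote 6).
- Extension: four-weekly for responders with marrow blasts below 5% (Protocol synopsis, time plan). For responders at or above 5% the interval is blacked out; I assume it stays two-weekly, since Part 2b schedules a dose at every visit.
- Horizon: a continued responder is evaluated 6 months after the primary period (Protocol 10.12). Counting 24 weeks from week 17 gives week 41.
- No delays, omissions or reductions.

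**Check of the map.** V1 to V4 give 4 doses before V5. Protocol VII, footnote 9, also puts the early assessment after 4 doses, so the map reproduces the one dose count the plan states.

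**Doses by V9.** 8 if the sum stops before the V9 infusion, 9 if it includes it.

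**Doses to week 41**
- Two-weekly: weeks 1, 3, …, 41 = (41 − 1)/2 + 1 = 21.
- Four-weekly after V9: 9 + weeks 21, 25, 29, 33, 37, 41 = 9 + 6 = 15.

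**Share missed** = 1 − (doses up to the cut-off)/(all doses). The cut-off is varied because the number is blacked out; V13 is week 25.

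| Last dose | After V9 | Doses given | Stops before V9 | V9 included | V13 included |
|---|---|---|---|---|---|
| Week 21 | two-weekly | 11 | 8 (27% missed) | 9 (18%) | 11 (0%) |
| Week 21 | four-weekly | 10 | 8 (20%) | 9 (10%) | 10 (0%) |
| Week 29 | two-weekly | 15 | 8 (47%) | 9 (40%) | 13 (13%) |
| Week 29 | four-weekly | 12 | 8 (33%) | 9 (25%) | 11 (8%) |
| Week 41 | two-weekly | 21 | 8 (62%) | 9 (57%) | 13 (38%) |
| Week 41 | four-weekly | 15 | 8 (47%) | 9 (40%) | 11 (27%) |

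At week 41 a V9 cut-off therefore counts 8/21 = 38% to 9/21 = 43% of doses two-weekly, and 8/15 = 53% to 9/15 = 60% four-weekly. With a constant dose per infusion, the same shares apply in milligrams.

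One consequence lies outside the extension phase. If the sum stops before V9, a non-responder dosed at V9 while awaiting the result is also undercounted: 8 of 9, or 11% missed.

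**The case against.** The strongest reply is that the cut-off may be deliberate. A fixed window matching the compliance window gives a like-for-like comparison of the primary phase between cohorts. Protocol 10.9.2 leaves details to the SAP, so the SAP does not contradict it. Later exposure is not lost either: duration runs on, dose intensity is shown by cycle, and Listings 16.8.1 and 16.8.2 have no stated cut-off. All of this stands, and it limits the harm. It does not explain why the restricted sum carries the unrestricted name, or why no whole-treatment total sits beside it. A listing does not correct a summary table.

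The cut-off number is also hidden, and the blackout is not a fault of the plan. If it hid the end-of-treatment visit, the point would fall; but the SAP elsewhere calls that the EOT visit.

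A reader might infer more than the documents support:
- *That every extension patient is certainly affected.* This needs a cut-off at V9 or earlier. With V13 included, a patient whose last dose is in week 21 loses nothing.
- *That Table 14.8.1 is the denominator for adverse-event rates, or that a dose-over-duration ratio will be biased.* Neither analysis is planned. TEAEs are tabulated as subjects and events, and dose intensity is the dose level administered, which does not use the truncated sum.
- *That interrupted infusions count in full because the SAP says calculated dose.* The same phrase also says the dose was administered, and no passage states how partial infusions are recorded.
- *That leaving out Part 2c doses is an error.* Protocol 5.1.4 and 8.1.6, and the matching SAP text, say data on these patients may be collected with no effect on the statistical analyses. Leaving them out is arguably intended. However, Part 2c schedules drug accountability and AE assessment, and neither the duration nor the TEAE definition excludes these patients, so treatment across the outputs is unclear.

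**Conclusion.** The mismatch is real and minor. Total dose has a visit cut-off; duration in the same table does not. Since the extension is open-ended, any numbered visit truncates the total for patients dosed beyond it.

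The size depends on the hidden visit and on time on treatment: from nothing for a patient who stops before the cut-off, to 57-62% missed (two-weekly) or 40-47% (four-weekly) at week 41 with a V9 cut-off. These figures rest on the dosing intervals and full adherence assumed above, and they describe the current regimen rather than Cohort 1. V9 is the likeliest reading, not an established one.

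The consequence is confined to one descriptive safety summary. The primary endpoint, the secondary efficacy analyses and the decision rules are untouched.

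**What to change.** In SAP 6.2.3, define total dose as the sum of doses administered from the first to the last infusion, extension phase included, with the same end point as duration of treatment in 7.7.3. In Table 14.8.1, keep the visit-limited sum as a separate row labelled 'total dose, primary phase', for comparing cohorts over a common window. State whether Part 2c doses are included, and apply the same rule to duration and TEAEs.

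The cost is one SAP line and one table row. Drug accountability is already scheduled at dosing visits in Parts 1, 2a, 2b and 2c, so no new data are needed. No dose or clinical rule changes.

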## 7. Data Handling

### 7.1 Handling of Missing Data and Outliers

If outliers, i.e., impossible, or very implausible values, occur, queries will be raised to the investigator who will either correct or confirm the value. If the value is confirmed, the analysis will be carried out with the outlier included. Complete exclusion of values should only be done in exceptional cases and is only valid for impossible and very implausible values with obvious justification. The decision to exclude data points from the statistical analysis is the joint responsibility of the sponsor, and the statistician. Outliers will be documented and, if applicable, their exclusion from analysis will be justified in the clinical study report.

Missing data will not be imputed.

## 7.2 Handling of Screening Failures, Withdrawals and Drop-outs

Data of withdrawals and drop-outs will be used as available.

Screening failures, i.e., subjects who have signed informed consent form but terminated the study for any reason before the first treatment will be replaced.

For all subjects determined as screening failures the following information is to be captured in the subject's source documents and eCRF page(s): the date informed consent form (ICF) was signed, demographics, the reason subject did not qualify for the study, and the investigator's signature for the eCRF pages.

A subject who discontinues study treatment prematurely for any reason is defined as "dropout" if the subject has already received study medication.

In all cases, the reason for study discontinuation must be recorded in the eCRF and in the subject's medical records.

Subjects who prematurely discontinue participation before end of treatment will not be replaced.

## 7.3 Data Review

Data are checked and cleaned during the course of the study. Protocol deviations such as time window deviations are identified during monitoring and by data management checks. The statistical programmer will collect the protocol deviations. Additional protocol deviations might be identified and added during this data review.

Classification of protocol deviations into critical and non-critical will be discussed between Sponsor and statistician prior to database lock, with the final decision being made by the Sponsor. A critical protocol deviation is defined as protocol deviation which might influence the outcome of the primary analysis (e.g., a violation of eligibility criteria detected after enrolment). The free choice of subjects to terminate their study participation prematurely is described in the study protocol and thus not regarded as protocol deviation but as reason for exclusion from the per protocol set. The following list of criteria can be used to identify critical protocol deviations and is not meant to be exhaustive:

- Violation against eligibility criteria
- Deviation from visit window of primary endpoint visits.
- Assessment of primary endpoint not performed
- Use of disallowed concomitant medication

For further details it is referred to the Data Review Meeting Plan (DRM).

## 7.4 Date Coding and Day Numbering

The format for presentation of date variables will be DDMMYYYY (e.g., 21JAN2021). The format for presentation of time variables will be hh:mm (e.g., 09:02).

If dates are partially given, they will not be completed unless relevant to calculate durations. For such cases, a worst-case scenario will be assumed as follows:

- If the duration of an adverse event is calculated, the date is imputed to yield the highest possible duration.
- If the time to onset of an adverse event is calculated, the date is imputed to yield the shortest time to onset.

Deviations will be documented and explained. For date imputations related to medical history/concomitant diseases or prior/concomitant medication, refer to sections 7.5.2 and 7.5.4, respectively.

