### 7.5.4 Separation of Previous and Concomitant Medications

Separation of previous from concomitant medications will be done by comparison of the stop date of the medication with the date of the first treatment with study medication. Each medication will be allocated unambiguously either to previous or concomitant medications:

- **Previous medication:** If the stop date is before start of treatment or the stop date is partially given and unambiguously before the start of treatment, the medication is allocated to previous medications.
- **Concomitant medication:** If the stop date is at or after the start of treatment or the medication is ongoing, the medication is referred to as concomitant medication. If the stop date is partially given and not unambiguously before start of treatment, the medication is allocated to concomitant medication. If the stop date is missing and the medication is not known to be ongoing, the worst case is assumed, and the medication is allocated to concomitant medication.

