#### 7.7.11 Time to Onset and Duration of Adverse Events

##### Time to onset of AEs

The following formula will be used to calculate the time to onset of AEs:

$$\text{Time to onset [days]} = \text{start date} - \text{date of first treatment} + 1$$

This formula can be used analogously whenever the time of onset must be calculated.

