### 7.7.12 Adverse Event and Toxicity Classification

An adverse event will be classified as a treatment emergent adverse event (TEAE) when it occurs only after treatment with IMP has started or is an already present event that worsens either in intensity, frequency during or following the treatment or changed from being not suspected to being suspected following the treatment.

Treatment emergent adverse events will be grouped into related and unrelated TEAEs. All TEAEs that are at least possibly related (Possible related, Probable related, Related) to the treatment or with missing assessment of the relationship will be categorized as related. All other TEAEs will be regarded as unrelated to the treatment.

For the purpose of ranking the severity of an TEAE and the toxicity, the categories will be ordered as following, from lowest to highest severity according to CTCAE v5.0:

- Grade 1 (Mild)
- Grade 2 (Moderate)
- Grade 3 (Severe)
- Grade 4 (Life threatening consequences)
- Grade 5 (Death related to AE)

TEAE occurring before visit [REDACTED] will be accounted for early toxicity.

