### 8.5.1 Analysis of AEs

The analysis of AEs will be based on the SES. In this trial, only TEAE's (see section 7.7.12) will be analyzed. TEAEs will be classified by system organ class and preferred term using the Medical Dictionary for Regulatory Activities (MedDRA).

An overview of the subjects experienced an TEAE and the number of TEAE will be tabulated. Additionally, TEAE will be summarized by relation to IMP, toxicity (severity), special interest (AESI) and early toxicity.

Individual listings of AEs, SAEs and deaths will be generated.

TEAEs leading to premature discontinuation of study drug or withdrawal from the study will be listed in the same manner.

Table	
14.7.1	TEAEs by SOC and PT, overall
14.7.2	TEAEs by SOC and PT, by relationship
14.7.3	TEAEs by SOC and PT, by toxicity
14.7.4	TEAEs by SOC and PT, by early toxicity
14.7.5	TEAEs by SOC and PT, by special interest
Listing	
16.7.1	Adverse events
16.7.2	Serious adverse events
16.7.3	Adverse Events leading to discontinuation
16.7.4	Death

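### The SAP's rule for partial adverse-event onset dates has no floor at first dose, and no rule fixes treatment-emergent status when the onset date is partial

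*SAP*

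**What the plan says.** SAP 7.4 limits when partial dates are completed: "If dates are partially given, they will not be completed unless relevant to calculate durations". Where completion is needed, it announces a worst-case approach with two rules for AEs. For duration: "If the duration of an adverse event is calculated, the date is imputed to yield the highest possible duration". For onset: "If the time to onset of an adverse event is calculated, the date is imputed to yield the shortest time to onset". It names no calendar day and gives no lower bound. It adds: "Deviations will be documented and explained".

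SAP 7.7.11 computes time to onset as the start date minus the date of first treatment plus 1, so an event on the day of first dose has the value 1. SAP 7.7.13 uses the same form for time to first related TEAE of grade 3 or higher, and SAP 8.5.2 analyses that time by Kaplan-Meier.

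On classification, SAP 7.7.12 says: "An adverse event will be classified as a treatment emergent adverse event (TEAE) when it occurs only after treatment with IMP has started". It also admits events already present that worsen, or that become suspected, following treatment. It does not mention partial dates. SAP 8.5.1 restricts the AE analysis: "only TEAE's (see section 7.7.12) will be analyzed". Protocol 9.3 keeps events that began before the first dose, and did not become more severe afterwards, out of the TEAE incidence tables.

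For medications, SAP 7.5.4 does state a default: "If the stop date is partially given and not unambiguously before start of treatment, the medication is allocated to concomitant medication". SAP 7.5.2 has the parallel rule for diseases.

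**The concern.** A rule presented as worst case should not move a possible toxicity to a date before treatment began. AEs are recorded from consent (Protocol 9.3, SAP 2.1.5) and screening may last up to 35 days (SAP 2.1.1). A pre-dose onset is therefore a legitimate value in this database, and nothing in SAP 7.4 stops the minimisation at the first dose.

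Two things are at stake. First, the time to first related grade 3 or higher TEAE can take a value before its own time origin. Second, a programmer who has only a month for the onset must still decide whether the event is a TEAE, and the SAP gives no rule for that decision. A month-only event in the month of first dose, if it truly followed the dose, began within 31 days of it. That is roughly the period of the early-toxicity summary, which SAP 6.2.2 runs to visit 3 (week 5).

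**Working it through.** The documents give no figure on this point, so there is none to reproduce. The check applies the SAP's formula to the case in question.

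**Inputs**
- Formula: start date - first-dose date + 1 (SAP 7.7.11; same form in 7.7.13).
- Rule: choose the date giving the shortest time to onset (SAP 7.4).
- Collection from consent (Protocol 9.3, SAP 2.1.5); screening up to 35 days (SAP 2.1.1).
- Assumed, because not in the documents: onset known to month and year only, in the month of first dose; first dose on day d; consent c days before first dose.

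**Literal reading, no lower bound.** The earliest compatible day is the 1st, so time to onset = 1 - d + 1 = 2 - d.

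| First dose on day d | Time to onset | With floor at first dose |
|---|---|---|
| 1 | 1 | 1 |
| 2 | 0 | 1 |
| 10 | -8 | 1 |
| 15 | -13 | 1 |
| 28 | -26 | 1 |
| 31 | -29 | 1 |

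The value is zero or negative for every d of 2 or more. In a non-leap year that is 365 - 12 = 353 of 365 possible first-dose dates (96.7%). This is a share of calendar dates under this reading, not a share of events.

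**Earliest day limited to consent.** The imputed date is the later of the 1st and the consent date, so time to onset is the larger of 2 - d and 1 - c.
- d = 15, c = 5: larger of -13 and -4, giving -4.
- d = 15, c = 20: larger of -13 and -19, giving -13.
- d = 31, c = 10: larger of -29 and -9, giving -9.

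The result exceeds zero only if d = 1 or c = 0.

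**Other cases**
- Onset known only as February, first dose 15 January: 1 February is 17 days later, so 17 + 1 = 18. No problem arises.
- Onset known only to the year, first dose 15 June: -164 with no bound, or -34 with consent 35 days earlier. The problem is the same.

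**With the floor.** If onset is the later of the first-dose date and the earliest compatible date, the month-of-first-dose case gives 1 for every d from 1 to 31.

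**Classification.** Two courses are open for an event dated March with a first dose on 15 March:
- If the imputed 1 March is used to classify, Protocol 9.3 treats the event as pre-treatment unless its severity later increased. SAP 7.7.12 would also keep it if it became suspected after treatment.
- If the imputed date is not used, the SAP offers no rule. Should the event then be counted as a TEAE, and be related and of grade 3 or higher, the literal rule gives it -13 in the analysis of SAP 8.5.2.

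**The case against.** The strongest reply is that the documents do not send the imputed date into the TEAE classification. SAP 7.4 completes dates only for durations, treatment-emergent status is not a duration, and SAP 7.7.12 never mentions imputation. This is correct. A reader might infer that affected events lose treatment-emergent status and vanish from Tables 14.7.1 to 14.7.5. The text does not support that as a consequence of the plan. It would happen only if programmers reused the date for a purpose that 7.4 does not name, and only for events that neither worsened nor became suspected. AE listings (16.7.1, 16.7.2) would still show them.

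Second, the shortest onset time can be read as day 1 for an event already counted as a TEAE. SAP 7.7.13 selects TEAEs before computing the time, and this reading suits the stated worst-case purpose. It is reasonable, but it is not written down, and it presupposes a classification that has no rule for partial dates.

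Third, SAP 7.5.2 and 7.5.4 work on stop dates, so they do not contradict 7.4. That is fair: they show the plan's general convention, and AEs lack a counterpart.

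Fourth, partial dates may be few. Subjects are asked about AEs at each visit (Protocol 9.3), the primary-phase schedule shows visits every two weeks, and data queries are planned (Protocol 11.2). For serious events, Protocol 9.3 does not collect those between consent and first dose unless a protocol-required procedure may have caused them, so a recorded serious event is usually post-dose. These facts limit the size of the problem. They also favour treatment-emergent as the default.

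**Conclusion.** The gap is real and small. SAP 7.4 has no floor at first dose, and no passage settles TEAE status for a partial onset date. Read literally, the rule gives an invalid event time for a month-only onset in the month of first dose, except when the dose is on the 1st or consent is on the dosing day. The one planned analysis clearly exposed is Table and Figure 14.7.6, time to first related grade 3 or higher TEAE. Loss from the other TEAE tables is possible but conditional on how the date is programmed.

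The size cannot be stated, because neither the number of partial AE dates nor whether the eCRF accepts them is given. The 96.7% should not be read as a share of events affected. For scale only: if one patient's sole grade 3 or higher event were lost, the observed proportion would fall by 1/22 = 4.5 to 1/10 = 10 percentage points for assumed cohort sizes of 22 down to 10 (1/20 = 5 points at 20). The current cohort size is blacked out; the range uses numbers from Protocol 10.3. The primary endpoint is not touched, and the trial is now exploratory throughout (Protocol 10.1).

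**What to change.** Add two sentences to the SAP, in 7.4 and 7.7.12:

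- An AE with a partial or missing onset date is classed as treatment-emergent unless the known parts of the date, or the stop date, place it unambiguously before the first dose. This follows the convention of 7.5.2 and 7.5.4.
- For such events, onset is imputed as the later of the first-dose date and the earliest date compatible with what is known.

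The cost is a change to one date derivation. SAP 2.10 allows updates of this kind before database lock. The downside is that a few true screening-period events with partial dates will count as TEAEs; flagging imputed onset dates in Listing 16.7.1 would let a reader see which ones.
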